12.4 Definition of Visit Windows

Data will be summarized and analyzed based on the list of visits specified in the schedule of assessments (SOA) of the protocol. All the post-baseline records will be assigned to an appropriate analysis visit using the rules below:

- For the post-baseline visits, the lower and the upper bound for the analysis visit windows
 are defined as the midpoints of the target date of the scheduled visits.
- If the date of assessment falls in between the lower bound and the upper bound for a visit
 as specified in the schedule of assessments of the protocol, then it will be assigned to that
 visit.
- If the interval separating 2 scheduled visits is an even number of days, the middle day will be included in the lower bound of the next visit.

• End of Treatment visit for subjects who discontinued the study early and unscheduled visits will be mapped to post-baseline scheduled visits if they fall in a scheduled visit window. If assessment result is available in the original post-baseline scheduled visit, then the record will be used in the analysis. If assessment from the original post-baseline scheduled visit is unavailable, then the assessment result mapped from unscheduled/end of treatment visit will be used for analysis. If there are more than one unscheduled/end of treatment visits mapped to the same window, the one closer to the target day will be used for analysis. If more than one visits have the equal distance to the target day, then the earlier one will be used for analysis. If more than one visits on the same day, the time or the sequence number will be used to select the earlier record. If more than one visits on the same day and could not be differentiated by the time or the sequence number, mean value will be used for analysis.

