7.2 Clinical Laboratory Data

The detailed lab parameter list is summarized in Table 2 (Page 47) of study protocol APL9-COV-201 amendment 3. Continuous laboratory parameters will be normalized by converting values in original units to values in SI units and classified as normal, abnormal low, or abnormal high on normal ranges supplied by the local laboratories and upon employing standardization.

Observed values and change from baseline of clinical laboratory data (serum chemistry, hematology, coagulation, complement activation and inflammation, and continuous urinalysis parameters) will be summarized at each analysis visit. Categorical laboratory data will also be tabulated by the number and percentage of patients of each category at each analysis visit.

Frequency of abnormal (out-of-range) laboratory values will be tabulated by analysis visit.

If lab values are beyond detectable limit, the detectable limits will be used for analysis. The original collected values will be presented in the listings.

Clinical laboratory data will be presented in listings. Out of range laboratory results with their corresponding changes from baseline will be listed in separate listings.

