8. PHARMACOKINETIC ANALYSIS

8.1 Drug Concentration

The observed values and changes from baseline of APL-9 concentrations will be summarized for pharmacokinetic (PK) set at each scheduled time point using descriptive statistics (including at least mean, SD, CV, Min, Max, Geometric Mean, and %CV). The number and percentage of subjects with a BLQ value will also be tabulated. The handling of BLQ in the summary table is described in Section 8.2.

Linear and log-linear individual concentration profile plots against the actual study visit will be produced by study part and treatment group.

Linear and log-linear mean concentration plots against the actual study visit will be generated by study part and treatment group. The number of subjects contributing to each mean value at a visit will be presented above the x-axis.

A listing of concentration data will be presented by study part and treatment group. The actual time, deviation, and percent deviation from nominal time will be listed.

All summaries and analyses of the pharmacokinetic data will be based on the PK set.

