9. PHARMACODYNAMIC ANALYSIS

9.1 Pharmacodynamic Data

The pharmacodynamic (PD) endpoints will be evaluated using the PD Population.

Observed values, changes from baseline and percentage changes from baseline in PD endpoints will be summarized by study part and treatment group at each protocol specified time point using descriptive statistics. PD markers include the following:

- complement activation (C3, C3a, C4, C4a, Bb, C5a, TCC, and alternative complement pathway hemolytic activity [AH50]),
- coagulopathy (reticulocyte count, schistocytes, lactate dehydrogenase, D-dimer, ferritin, haptoglobin, fibrinogen),
- inflammatory cytokines (C-reactive protein, tumor necrosis factor α , IL-1 β , and IL-6).

Spaghetti plots for individual observed values and individual changes from baseline will be presented graphically. Actual sampling times will be used for the graphical presentation of individual data

Observed values, changes from baseline, and percentage changes from baseline will also be presented graphically by study part and treatment group. Nominal sampling times will be used for the display in plots.

PD parameters will be listed together with changes from baseline and percentage changes from baseline by study part and treatment group.

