12.5 Repeated or Unscheduled Assessments

For repeated measurements with more than one evaluable result at the same visit, mean value will be used for analysis. For repeated measurements with only one evaluable result at the same visit, then the evaluable assessment will be used for analysis. For unscheduled measurements, the records will be mapped to scheduled post-baseline visits according to visit windows described in section 12.4 above.

The repeated and unscheduled measurements will be presented in the listings.

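### SAP 12.4 and 12.5 assign unscheduled samples to visits by date without checking treatment status, so in Part 2 an off-drug discharge sample can be summarized as Day 11 or Day 15 PK/PD

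*SAP*

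**What the plan says.** **Sampling.** Protocol 11.5 sets PK samples on Days 1, 3, 5 and 7, on Days 11 and 15 only while the infusion is still running, and at the end-of-treatment (EOT) visit. Protocol 11.6 ties PD sampling to the same times. If discharge comes after EOT, one more PK/PD sample is taken on the day of discharge. Protocol Table 1, footnotes m and n, have it recorded as an unscheduled visit.

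**Visit assignment.** SAP 12.4 begins: "All the post-baseline records will be assigned to an appropriate analysis visit using the rules below". It then says that "unscheduled visits will be mapped to post-baseline scheduled visits if they fall in a scheduled visit window". A scheduled result has priority. If there is none, "then the assessment result mapped from unscheduled/end of treatment visit will be used for analysis". SAP 12.5 repeats the rule: "For unscheduled measurements, the records will be mapped to scheduled post-baseline visits according to visit windows described in section 12.4 above".

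**Summaries.** PK concentrations "will be summarized for pharmacokinetic (PK) set at each scheduled time point using descriptive statistics" (SAP 8.1). PD markers "will be summarized by study part and treatment group at each protocol specified time point using descriptive statistics" (SAP 9.1), and for the PD group plots "Nominal sampling times will be used for the display in plots".

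**Expected recovery.** Protocol 7.3 expects complement function to be back to normal within 24 hours of stopping the drug.

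**The concern.** The Day 11 and Day 15 PK/PD slots are meant for subjects who are on infusion. A subject who has stopped has no scheduled sample there by design, and that is exactly the condition under which 12.4 lets an unscheduled result step in. The discharge-day sample is the one most likely to do so, and it is off drug.

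PK and PD are secondary endpoints. An off-drug value in the APL-9 arm moves the complement summary toward no effect and would be expected to lower the PK mean. Sustained inhibition during infusion could then be read as waning at Day 11 or Day 15. For the coagulation and inflammation markers the direction is not known.

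**Working it through.** The plan gives no figure for this, so the check applies its rules to its own schedule.

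**Inputs.** PK/PD days 1, 3, 5, 7, 11 and 15 (Protocol 11.5). Table 1 columns for Days 8-10, 11, 12-14, 15 and 16-21, headed as Part 2 only. Window bounds at the midpoints between visits, with the middle day of an even interval going to the later visit (SAP 12.4).

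**Step 1: is the slot empty?** For a subject off infusion before Day 11, no Day 11 or Day 15 PK/PD sample is due. The priority of scheduled results therefore blocks nothing. Where a scheduled result does exist, it is never displaced.

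**Step 2: which discharge dates fall in the slot?** SAP 12.4 does not say whether the grid is every study day, the Table 1 columns, or only the days on which that assessment is due. The last column of the table takes a last infusion on Day 7 and subtracts 7 from the sample day.

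| Reading of the grid | Dates labelled Day 11 | Dates labelled Day 15 | Days since last infusion (Day 11; Day 15) |
|---|---|---|---|
| Each study day is its own visit | 11 | 15 | 11-7 = 4; 15-7 = 8 |
| Table 1 columns, ranges centred at Days 9, 13 and 18 (assumption) | 10-11 | 14-16 | 3-4; 7-9 |
| PK/PD days only | 9-12 | 13 onward | 2-5; 6 or more |

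Second row: (9+11)/2 = 10 goes to Day 11; (11+13)/2 = 12 goes to Day 13; (13+15)/2 = 14 goes to Day 15; (15+18)/2 = 16.5, so Day 15 ends at Day 16. Third row: (7+11)/2 = 9 goes to Day 11; (11+15)/2 = 13 goes to Day 15. On that grid Day 15 has no upper bound. If Day 51 is taken as the next target, (15+51)/2 = 33 and Day 15 runs to Day 32.

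On every reading an off-drug sample can fall in both slots, and every interval in the last column is longer than 24 hours.

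**Step 3: later stops.** Suppose the last infusion is on Day 10 and discharge is on Day 11. The discharge sample is 1 day off drug. If the EOT sample of Day 10 is mapped to the same window, the record nearer the target is used: |10-11| = 1 against |11-11| = 0. The off-drug sample is chosen.

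**Step 4: scope.** Part 1 has no Day 11 or Day 15 visit. Subjects whose EOT and discharge fall on the same day have no extra sample and are not affected.

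**The case against.** **The PK and PD sections may not use the mapping.** SAP 7.2 to 7.4 summarize by analysis visit, the unit that 12.4 defines. SAP 8.1 and 9.1 instead use the scheduled or protocol-specified time point, and the protocol calls the discharge sample unscheduled. This stands to the extent that entry into those tables is not certain. But 12.4 covers every post-baseline record and turns an unscheduled record into a scheduled-visit value, and neither 8.1 nor 9.1 excludes mapped records. The more natural reading lets them in.

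**Table 1 has its own column for EOT and discharge day, with PK/PD marked.** That could be a home for the sample. Footnotes m and n nevertheless record it as unscheduled, and the SAP does not direct it to that column.

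**Dosing may run until discharge.** Protocol 7.1 and SAP 3.1 continue Part 2 dosing to the last of Day 7, end of respiratory support, or discharge, so EOT and discharge would often coincide. Protocol 9.1.1 and 10.1 cap dosing at the period the DMC has allowed, and subjects who stop early stay in the study. These passages conflict. The footnotes themselves provide for different days.

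**The values can be traced.** The PK tables count results below quantification, the PK listing shows actual time and deviation, individual PD plots use actual times, and unscheduled results are listed. This helps a careful reader, but no summary table separates off-drug values.

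**The laboratory tables.** A reader might extend the point to SAP 7.2, where "coagulation, complement activation and inflammation, and continuous urinalysis parameters) will be summarized at each analysis visit". The documents do not support calling those Day 11 and Day 15 visits on-treatment: the laboratory row of Table 1 and Protocol 11.1.8 do not make them depend on ongoing treatment. A by-calendar-day laboratory summary that includes subjects off drug is legitimate.

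**Conclusion.** The gap is real but limited. SAP 12.4 and 12.5 contain no treatment-status condition, and as written they can place an off-drug discharge sample in the Part 2 Day 11 or Day 15 PK/PD summary. This rests on two assumptions: that 8.1 and 9.1 take their values after the 12.4 mapping, and that some subjects end treatment before discharge.

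Three stronger readings are tempting and are not supported:

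- That contamination is certain. The wording of 8.1 and 9.1 leaves room for exclusion.
- That it is frequent because, of discharge Days 8 to 21, 4 + 9 = 13 of 14 map to Day 11 or Day 15 on the PK/PD-day grid. The count is 2 + 3 = 5 on the column-centred grid and 2 if each day is a visit, and it counts dates, not subjects.
- That the dilution can be quantified. If a share f of APL-9 values in a cell is off drug and carries no drug effect, the table shows (1-f) of the on-drug effect. The documents give no discharge distribution and conflict on when dosing ends, so neither f nor the number of subjects can be computed.

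The affected summaries are descriptive. No hypothesis test and no part of the primary safety endpoint changes. The point merits a change to the SAP before programming and does not threaten the trial's main conclusions.

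**What to change.** - In SAP 12.4 and 12.5, for PK and PD endpoints, map a sample to Day 11 or Day 15 only if it was drawn during infusion or on the last infusion day.
- Summarize discharge samples taken after EOT as a separate post-treatment time point, by time since last dose. This keeps every value and shows recovery off drug.
- State in 12.4 which grid defines the windows, and in 8.1 and 9.1 whether mapped unscheduled samples enter the tables.
- Reconcile Protocol 7.1 and SAP 3.1 with Protocol 9.1.1 and 10.1 on when Part 2 dosing ends.

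The cost is SAP wording and a last-dose flag. Dose date, time and duration are already recorded (Protocol 9.4), and SAP 8.1 and 9.1 already rely on actual sampling times. The downside is fewer values at Day 11 and Day 15.

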12.5 Repeated or Unscheduled Assessments

For repeated measurements with more than one evaluable result at the same visit, mean value will be used for analysis. For repeated measurements with only one evaluable result at the same visit, then the evaluable assessment will be used for analysis. For unscheduled measurements, the records will be mapped to scheduled post-baseline visits according to visit windows described in section 12.4 above.

The repeated and unscheduled measurements will be presented in the listings.

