#### 11.1.8. Clinical Laboratory Tests

Laboratory test samples (Table 2) are to be obtained at designated visits as detailed in the SoA (Table 1). Blood will be collected 3 times on Day 1: (1) once prior to administration of the APL-9 bolus, (2) once as soon as possible following the bolus (within 5-10 minutes) prior to the continuous infusion, and (3) once at 2 hours after the beginning of the continuous infusion. Following that, assessments should be collected within the time frame of each calendar day.

Blood samples will be analyzed at one or more central (or local) laboratory facilities, as defined in the laboratory manual. All laboratory reports must be reviewed, signed, and dated by the investigator. A legible copy of all reports must be filed with both the subject's eCRF and medical record (source document) for that visit. Any laboratory test result considered by the investigator to be clinically significant should be considered an AE (clinically significant AEs include those that at minimum require an intervention). Clinically significant abnormal values occurring during the study will be followed up until repeat test results return to normal, stabilize, or are no longer clinically significant.

Instructions for collection, handling, processing, storage, and shipping of samples will be provided in a separate laboratory reference manual prior to study initiation.

PARAMETERS ANALYZED AT	THE LOCAL LABORATORY	
Blood/serum/plasma samples		
Hematology	Serum chemistry	
ABG	Albumin	Ferritin
Hb	ALT	Glucose
Hematocrit	ALP	Haptoglobin
Platelet count	AST	HDL
RBC count	Bicarbonate	Iron
Reticulocyte count	Bilirubin (total, direct, and indirect)	LDH
Schistocytes	BUN	LDL
WBC count with differential	C-reactive protein (CRP)	Phosphorus
	C3 and C4	Potassium
Coagulation panel a	Calcium	Pregnancy
D-dimer	Chloride	Sodium
Fibrinogen	Creatinine	Total cholesterol
INR	Creatine kinase	Total protein
PT	Cystatin C	Triglycerides
	eGFR	Troponin
		Uric acid
Urine samples		
Urinalysis		
Bilirubin		Nitrite
Blood		pН
Glucose		Protein
Ketones		Specific gravity
Leukocyte esterase		Urobilinogen
-	sediment, including for presence of	
	performed on all abnormal urinalyses	
Respiratory swab	· · · · · ·	
Viral RNA or viral antigen assessme	nt	
SARS-CoV-2		
PARAMETERS ANALYZED AT	CENTRAL/SPECIALTY LABORATO	RIES
Plasma samples		
Complement biomarkers	Inflammation biomarkers CC	
Bb, C3a, C4a, C5a, TCC	TNFα	
	IL-1β	
	IL-6	
Serum samples		
PK concentrations		
AH50		

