## 12.4. Safety Analysis

All safety analyses will be summarized for the safety set.

Adverse events will be coded using MedDRA. All AEs, including TEAEs, will be summarized by System Organ Class, Preferred Term, and treatment group for number of subjects and proportion reporting the event. A similar summary will be produced for SAEs, AEs leading to termination, severe AEs, and AEs related to the investigational product. The intensity of AEs and the relationship to investigational product will be summarized for each System Organ Class and Preferred Term by treatment group.

Withdrawals because of AEs will be summarized for each body system and Preferred Term by treatment group.

As described in Section 11.2, TEAEs are defined as those AEs that develop or worsen after the first dose of study medication up to and including the safety follow-up assessment 30 days after the last dose of study drug (up to Study Day 51 with a +7-day window).

AE summaries will be presented across all subjects. All AEs will be listed by subject, along with information regarding onset, duration, relationship, and severity to investigational product, action taken with investigational product, treatment of event, and outcome.

All laboratory assessments will be summarized by treatment group using appropriate descriptive statistics.

Changes from baseline in clinical laboratory tests will be summarized, using descriptive statistics, by visit and nominal time after dosing, and by treatment group. Baseline will be taken as the last predose assessment. Out-of-range values will be flagged in data listings.

Changes from baseline in vital signs will be summarized, using descriptive statistics, by treatment, visit, and nominal time after dosing. Baseline will be taken as the last predose assessment.

Values of potential clinical significance will be flagged in listings and summarized by treatment.

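### By-visit rules can leave off-schedule abnormal laboratory and ECG results, and the post-dose Day 1 laboratory draws, out of the SAP's safety tables, with no departure from Protocol 12.4 recorded

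*SAP*

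**What the plan says.** For laboratory data, SAP 7.2 states: "Frequency of abnormal (out-of-range) laboratory values will be tabulated by analysis visit". SAP 7.4 counts abnormal ECG interpretations in the same way. Neither section plans a worst post-baseline value, an any-time abnormality count or a shift table.

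Two other sections decide which records reach an analysis visit. SAP 12.4 gives the scheduled record precedence: "If assessment result is available in the original post-baseline scheduled visit, then the record will be used in the analysis". Otherwise, "If assessment from the original post-baseline scheduled visit is unavailable, then the assessment result mapped from unscheduled/end of treatment visit will be used for analysis". Where several compete, "If there are more than one unscheduled/end of treatment visits mapped to the same window, the one closer to the target day will be used", with ties going to the earlier record. SAP 12.5 covers repeats: "For repeated measurements with more than one evaluable result at the same visit, mean value will be used for analysis". It also says: "The repeated and unscheduled measurements will be presented in the listings".

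The protocol asks for more. Its section 11.1.8 says "Blood will be collected 3 times on Day 1": before the bolus, within 5-10 minutes after it, and 2 hours into the continuous infusion. Its section 12.4 says: "Changes from baseline in clinical laboratory tests will be summarized, using descriptive statistics, by visit and nominal time after dosing, and by treatment group". It sets the same level of summary for vital signs, and it wants values of potential clinical significance both flagged in listings and tabulated per treatment.

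SAP section 1 says that its analyses replace those in the protocol. SAP 14.1, on changes from the protocol, says not applicable.

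**The concern.** Safety is the primary objective. A safety reader wants to know how many subjects in each arm had an abnormal value at any time, and how bad the worst one was. An unscheduled test is often taken because something looks wrong, yet that record is set aside whenever the scheduled one in its window exists. The mean of an abnormal value and a normal repeat can fall back inside the reference range. The two Day 1 draws after the loading dose are the only laboratory samples timed to show an acute effect, and the laboratory tables have no place for them. A reader of the SAP alone would not learn that the protocol had promised otherwise.

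**Working it through.** The plan gives no figure on this point. Its one calculation, the chance of at least one SAE among about 30 subjects per group, plays no part here. The check is to follow the rules through.

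**1. Laboratory windows.** Inputs: laboratory target days 1, 3, 5, 7, 11 and 15 (Protocol Table 1), and the SAP 12.4 midpoint rule, under which the middle day of an even interval goes to the later visit.

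| Visit | Lower midpoint | Days covered |
|---|---|---|
| Day 3 | (1+3)/2 = 2 | 2-3 |
| Day 5 | (3+5)/2 = 4 | 4-5 |
| Day 7 | (5+7)/2 = 6 | 6-8 |
| Day 11 | (7+11)/2 = 9 | 9-12 |
| Day 15 | (11+15)/2 = 13 | 13 onward |

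The end-of-treatment and discharge column has no fixed day and is not shown.

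**2. Day 1.** No post-baseline window contains Day 1. The protocol schedule has 2 (Day 1 post-bolus and 2-hour) + 3 (Days 3, 5, 7) = 5 post-dose laboratory points through Day 7; the windows give 3. The SAP does not say whether draws at different nominal times are repeats under 12.5, so the two draws are either unassigned or at risk of being averaged. PK (SAP 8.1) and PD (SAP 9.1) are summarized at scheduled or protocol-specified time points. The laboratory tests that are also PD markers, such as C3, C4, CRP, D-dimer, LDH, ferritin, haptoglobin and fibrinogen, therefore keep their Day 1 points there. Tests such as ALT, creatinine, potassium, troponin and platelets do not.

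**3. Which record enters the table.**

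| Records in the window | What is tabulated |
|---|---|
| Scheduled normal, unscheduled abnormal | The normal one; the abnormal one is left out |
| Scheduled abnormal, unscheduled normal | The abnormal one is kept |
| No scheduled result, several unscheduled | One: nearest the target day, then earlier |
| Same-day unscheduled results | The earlier; the mean only if order cannot be established |
| Several evaluable repeats at one visit | The mean |

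The first, third and fifth rows can lose or dilute an abnormal result.

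**4. Dilution.** If one of k averaged results exceeds the others by e, the mean exceeds them by e/k: half for k = 2, a third for k = 3. With assumed values of 6 × ULN once and 1 × ULN otherwise, the mean is (6+1)/2 = 3.5 × ULN or (6+1+1)/3 = 2.7 × ULN. Those means are still flagged, but lower. With two results, the flag disappears when the excess of one over the limit is smaller than the shortfall of the other below it.

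How often that happens depends on laboratory variability, which the documents do not give. As an illustration only, a simulation assumed normal values, an upper limit at 1.96 SD of a single result, and a within- to between-subject SD ratio from 0.3 to 1.0. Among subjects with at least one out-of-range result, the mean was out of range in 65% down to 26% (k = 2), or 55% down to 13% (k = 3).

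**5. ECG.** An interpretation of normal or abnormal cannot be averaged, so 12.5 affects only the interval summaries. Footnote f of Table 1 records the worst daily value of continuous variables, which limits dilution within a day. What remains is selection under 12.4. Footnote n makes daily ECGs after end of treatment unscheduled, so those mapped to a visit window are subject to the rules in step 3.

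**6. Protocol against SAP.** Nominal time appears in Protocol 12.4 for laboratory tests and vital signs; SAP 7.2 and 7.3 have analysis visits only. The SAP sets potential-significance criteria only for vital signs (its Table 2) and uses them as listing flags, with no table by treatment. SAP 14.1 mentions neither omission.

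**The case against.** The strongest reply is that nothing is lost from the report. Every repeat and unscheduled result is listed, out-of-range laboratory results have their own listing, and with about 30 subjects per arm a reviewer can read them all. The primary endpoint is the incidence of TEAEs and SAEs. Protocol 11.1.8 makes a laboratory result that the investigator judges clinically significant an AE, so it reaches the primary tables whatever 12.4 and 12.5 do. The DMC works from a separate analysis plan. Preferring the scheduled record in a by-visit table is ordinary practice, and the protocol never asked for a worst-value table as such.

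Most of this stands, and it limits the point. It does not remove it. Listings do not compare arms. The AE route depends on the investigator's judgment, and 11.1.8 ties clinical significance to events that at minimum need an intervention, so lesser excursions may appear in no table. The protocol did ask for potentially significant values to be summarized by treatment.

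A reader might also infer more than the text supports:

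- **That the rules systematically hide a difference between arms.** They apply alike to both arms, an abnormal scheduled value is retained, and no direction or size of bias can be derived from the documents.
- **That several days of ECGs are averaged into one value,** because Table 1 has single columns for Days 8-10, 12-14 and 16-21. The SAP does not say that a column is one visit, and footnotes f and n describe daily recording.
- **That a fixed share of short excursions is missed.** This would need the frequency of unscheduled sampling, the completeness of scheduled results and the timing of the end-of-treatment and discharge samples. Where no scheduled result exists, 12.4 brings an unscheduled one in.

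**Conclusion.** The point holds in a limited form. As written, the SAP can leave off-schedule abnormal results out of every between-arm laboratory and ECG table and can dilute repeated laboratory values. In the section 7.2 tables the two post-dose Day 1 draws have no post-baseline visit of their own (three post-dose points through Day 7 instead of five); PK and PD summaries are unaffected. Two summaries promised in Protocol 12.4 are dropped without being recorded. The count of five rests on Protocol Table 1 and section 11.1.8, and the count of three on the SAP 12.4 midpoint rule. The number of subjects affected cannot be estimated from the documents, and the dilution percentages rest on an assumed model. This is an inexpensive improvement to make before database lock. It does not threaten the primary endpoint.

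**What to change.** 1. SAP 7.2 and 7.4: add a by-arm table of subjects with any post-baseline abnormal value and of each subject's worst post-baseline value (high and low separately), using all scheduled, repeat and unscheduled records.
2. SAP 12.5: for by-visit safety tables, use a single scheduled record instead of the mean.
3. SAP 7.2: show the Day 1 predose, post-bolus and 2-hour laboratory draws as three separate nominal time points.
4. SAP 14.1: record any departure from Protocol 12.4 that remains, including nominal time for vital signs and the by-treatment summary of potentially clinically significant values if these are not restored.

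The cost is some SAP wording and a few extra tables from data already collected and listed. No sample-size or power figure changes.
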